6.4. End-of-Treatment/Early Termination (Visit 21; Week 52)

The following activities and/or assessments will be performed at the End-of-Treatment or Early Termination visit (Visit 21). No fasting is required prior to the End-of-Treatment visit.

- Assess for and record AEs
- Assess for and record concomitant medication use including allowable analgesics
- Review electronic diary data and collect electronic diary
- Collect study medication and review medication compliance
- Record vital signs (temperature, heart rate, supine and orthostatic blood pressure) and body weight
- Collect blood and urine samples for evaluation of standard laboratory safety tests (chemistry [hematology, and urinalysis). The central laboratory will perform a serum pregnancy test on all female subjects regardless of child-bearing potential
- Ask the subject to complete the PGIC, HADS, SF-36 and EQ-5D questionnaires
- Complete the C-SSRS (See Section 9.2.1)
- Perform complete physical examination for all subjects, including a fundoscopy examination with pupil dilation or a scanning laser ophthalmoscopy examination for de novo subjects only (see Section 9.9.2)
- Perform a 12-lead ECG (Section 9.8)
- Update IXRS with subject status

6.5. Follow-Up

6.5.1. Post-Treatment Follow-Up (Visits 22 to 24; Weeks 52 to 56)

6.5.1.1. Telephone Contact at Day 3 of Follow-up (Visit 22; Week 52.5)

All subjects, including those who discontinue prematurely, will be contacted by telephone 3 days after the subject's last dose of study treatment. The following activities and/or assessments will be performed at this 3-day follow-up telephone contact:

- Assess for and record AEs
- Assess for and record concomitant medication use including allowable analgesics
- Administer the PWC

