4.2.1. Reasons for Withdrawal/Early Discontinuation

If a subject discontinues from the study treatment for any reason, the reason for discontinuation or withdrawal must be recorded on the eCRF using the following criteria:

Subjects who did not complete one of the preceding Phase 3 DS-5565 studies (DS5565-A-E309, DS5565-A-E310, or DS5565-A-E311) and withdraw prior to start of treatment but after signing informed consent

- Did not satisfy all inclusion/exclusion criteria
- Adverse event
- Lost to follow-up
- Withdrawal by subject (indicate reason)
- Physician decision

For subjects discontinued or withdrawn after start of treatment but before completing the treatment period:

- Adverse event
- Death
- Lack of efficacy
- Lost to follow-up
- Protocol violation
- Study terminated by sponsor
- Withdrawal by subject (indicate reason)
- Other (indicate reason)

If a subject is withdrawn due to requirement for a prohibited pain medication, the reason may be recorded as lack of efficacy, as appropriate. Reasons recorded under "protocol violation" may include failure to comply with protocol requirements or study procedures, pregnancy, etc.

A subject may be withdrawn due to non-compliance with any aspect of the protocol, as determined by the investigator and/or the sponsor's medical monitor or designee. Subjects who miss > 7 days of consecutive doses of study medication should be withdrawn from the study and early termination study procedures performed.

All subjects who are withdrawn should complete protocol-specified withdrawal procedures (see Section 4.2.2 and Section 6.4).

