4.2.2. Withdrawal Procedures

If a subject withdraws (or is withdrawn) from the study, the investigator should complete and report all observations as thoroughly as possible up to the date of withdrawal, including the date of last treatment and the reason for withdrawal.

If the subject is withdrawn due to an AE, the investigator should follow the subject until the AE has resolved or stabilized.

All subjects who are withdrawn from the study should complete all end-of-treatment/early termination (Visit 21) procedures as soon as possible after early withdrawal (Section 6.4). All subjects who are withdrawn from the study should return for a post-treatment follow-up visit (Section 6.5).

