6.5.1.2. Visit at Week 2 of Follow-up (Visit 23; Week 54)

All subjects then will return to the clinic for post-treatment follow-up approximately 14 (\pm 3) days following the last dose of study medication.

The following activities and/or assessments will be performed at the Follow-up clinic visit (Visit 23, Week 54):

- Assess for and record AEs
- Assess for and record concomitant medication use including allowable analgesics
- Record vital signs (temperature, heart rate, supine and orthostatic blood pressure) and body weight
- Perform urine pregnancy test on all WOCBP and confirm negative
- Administer the C-SSRS(See Section 9.2.1)
- Administer the PWC

Any abnormal findings (including abnormal laboratory values) observed at the End-of-Treatment visit should be rechecked at the Follow-up visit. Further safety assessments may be required for clinically significant abnormal findings observed at the Follow-up visit.

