9.10.2. Physician Withdrawal Checklist (PWC)

The PWC will be administered by the investigator or designee using the study-specific tablet at the Post-treatment Follow-up visit. In addition, the PWC will be administered by telephone 3 days after the subject's last dose of medication.

Although developed specifically to measure symptoms of benzodiazepine withdrawal,¹⁴ the PWC also has been used in studies of pregabalin.^{15,16,17} The PWC rates 20 common symptoms of withdrawal. The symptoms measured are based on those that are

potentially related to benzodiazepine withdrawal: somatic, mood, cognitive, fatigue, and gastrointestinal.

Each of the 20 individual items on the PWC are rated as not present, mild, moderate, or severe. Individual items rated as mild, moderate, or severe should not be handled as individual TEAEs. Rather, for any subject with at least 1 individual item rated as mild, moderate, or severe, the investigator should report “withdrawal” as a TEAE.

In addition, the investigator should be particularly attentive to any potential TEAEs that suggest opiate withdrawal at the Follow-up visit.

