11.6.4. Electrocardiogram Analyses

ECG data will be listed and summarized by visit. Shift tables for ECG results (normal or abnormal) will be presented by treatment arm to show changes from baseline (normal or abnormal) to end-of-treatment (normal or abnormal).

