17.3. Schedule of Events

Table 17.1: Schedule of Events

Study Period	Screening/Baseline (De Novo Only)			Start of Tx	on-Treatment				End of Tx/Et	Follow-Up ^a		
	1	2	3		4	5	6-11	12		13-20	21	22
Telephone Contact	--	X	--	--	--	--	--	--	--	X		X
Week	-3	-2	-1	0	1	3, 5, 7, 9, 11, 13	16	20, 24, 28, 32, 36, 40, 44, 48	52	52.5	54	56
Visit Window (Days)	--	--	--	--	±3	±3	±3	±7	±7	±1	±3	±7
Informed consent	DN			X ^b								
Inclusion/exclusion	DN			X								
Demographic information	DN			X ^b								
Medical/surgical history	DN			X ^b								
Adverse event reporting		DN	DN	X ^c	X	X	X	X	X	X	X	X
Washout instructions		DN										
Concomitant medications	DN	DN	DN	X ^c	X	X	X	X	X	X	X	X
Vital signs	DN			X ^d	X	X	X	X	X		X	
Height	DN			X ^b								
Weight	DN			X ^d	X	X	X	X	X		X	
Physical examination ^e	DN			X	X	X	X	X	X			
Fundoscopy ^e	DN							DN (V.14)	DN			
C-SSRS	DN			X ^d	X	X	X	X	X		X	
WPI/SSS	DN											

Study Period	Screening/Baseline (De Novo Only)			Start of Tx	on-Treatment				End of Tx/Et	Follow-Up ^a		
	1	2	3		4	5	6-11	12		13-20	21	22
Telephone Contact	--	X	--	--	--	--	--	--	--	X		X
Week	-3	-2	-1	0	1	3, 5, 7, 9, 11, 13	16	20, 24, 28, 32, 36, 40, 44, 48	52	52.5	54	56
Visit Window (Days)	--	--	--	--	±3	±3	±3	±7	±7	±1	±3	±7
M.I.N.I	DN											
12-lead electrocardiogram	DN			X					X			
Clinical laboratory tests	DN			X ^d	X	X	X	X	X			
Pregnancy test ^f	DN			X ^d	X	X	X	X	X		X	

Table 17.1: Schedule of Events (Continued)

Study Period	Screening/Baseline (De Novo Only)			Start of Tx	on-Treatment				End of Tx/Et	Follow-Up ^a		
	1	2	3		4	5	6-11	12		13-20	21	22
Telephone Contact	--	X	--	--	--	--	--	--	--	X		X
Week	-3	-2	-1	0	1	3, 5, 7, 9, 11, 13	16	20, 24, 28, 32, 36, 40, 44, 48	52	52.5	54	56
Visit Window (Days)	--	--	--	--	±3	±3	±3	±7	±7	±1	±3	±7
PWC										X	X	
Study drug compliance					X	X	X	X	X			
Contact IXRS	DN			X	X	X	X	X	X			
Study drug dispensing ^g				X	X	X	X	X ^h				
PGIC									X			
HADS				X					X			
EQ-5D and SF-36				X					X			
Provide daily diary			DN									
Review/collect daily diary				X ⁱ		X ⁱ		X ⁱ	X ⁱ			
Pain intensity rating				X ⁱ		X ⁱ		X ⁱ	X ⁱ			
Sleep interference score				X ⁱ		X ⁱ		X ⁱ	X ⁱ			

DN denotes visits and assessments for de novo subjects only.

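### Subjects who stop for good and are found only through the missed-dose rule cannot have the Day 3 withdrawal checklist on time, and their late ECG counts as end-of-treatment

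*Combined protocol and SAP*

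**What the plan says.** Post-treatment follow-up is timed from the last dose. Section 6.5.1.1 sets the first contact (Visit 22): "All subjects, including those who discontinue prematurely, will be contacted by telephone 3 days after the subject's last dose of study treatment". Section 9.10.2 ties the checklist to the same day: "the PWC will be administered by telephone 3 days after the subject's last dose of medication". The second and last PWC is at Visit 23 (Section 6.5.1.2), nominally 14 ± 3 "days following the last dose of study medication". Table 17.1 gives Visit 22 a window of ±1 day and shows the PWC at Visits 22 and 23 only. It is not among the Visit 21 procedures in Section 6.4.

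Early termination is timed differently. Section 4.2.1 says "Subjects who miss > 7 days of consecutive doses of study medication should be withdrawn from the study and early termination study procedures performed". Section 4.2.2 adds "All subjects who are withdrawn from the study should complete all end-of-treatment/early termination (Visit 21) procedures as soon as possible after early withdrawal". Neither sets a limit relative to the last dose, although Section 4.2.2 does require the date of last treatment to be reported.

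Section 9.8 schedules ECGs at Visit 1 (de novo subjects only), Visit 4 and Visit 21. Section 11.6.4 tabulates shifts "to show changes from baseline (normal or abnormal) to end-of-treatment (normal or abnormal"), with no condition on time since last dose. Under Section 6.3, completers take their last dose on the evening before Visit 21.

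**The concern.** The follow-up clock starts at the last dose, while the missed-dose rule and the early termination visit start when the absence of dosing is long enough or becomes known. For a subject who stops silently, the first required follow-up contact is due before the rule that identifies the subject can be met. No section says what to do about the PWC in that case.

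The PWC and the ECG are both named components of the primary safety endpoint (Section 3.1.3). Section 1.3 lists abrupt or rapid discontinuation among the cautions for approved drugs of the class. Section 9.10.2 turns any positive PWC item into a reported withdrawal TEAE, so a checklist not given also removes that prompt. Under Section 11.2, percentages are taken over subjects assessed, so the Day 3 PWC result would describe mainly subjects whose stop was known promptly. In the ECG table, recordings made about one day after a dose would sit beside recordings made more than a week after one, which can blunt an on-treatment change.

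**Working it through.** The plan states no figure to reproduce. The check is date arithmetic on its own windows, counting days after the last dose.

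**Inputs**
- Visit 22: 3 ± 1 days (Section 6.5.1.1, Table 17.1), so Days 2 to 4.
- Visit 23: 14 ± 3 days (Section 6.5.1.2), so Days 11 to 17.
- Missed-dose rule: more than 7 consecutive days (Section 4.2.1), so the eighth missed day, about Day 8.
- Nominal clinic visits (Section 6): Weeks 0, 1, 3, 5, 7, 9, 11, 13 and 16, then every 4 weeks to Week 52.

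**Step 1: can Visit 22 be in window?** The gap is the earliest trigger minus the close of the window: 8 − 4 = 4 days too late. Reading the trigger as Day 7 or Day 9 gives 7 − 4 = 3 or 9 − 4 = 5 days. The answer is no on each reading, provided dosing has not resumed.

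**Step 2: how old is the Visit 21 ECG?** At least 8 days after the last dose for these subjects, against about 1 day for completers.

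**Step 3: is the Visit 23 PWC still possible?** This depends on when the subject is found, which the documents do not determine. Assume detection at the next nominal visit at which the rule is met, with last-dose days spread evenly over Days 0 to 355. For each last-dose day *t*, the lag is the first visit day *v* with *v* − *t* ≥ 8, minus *t*. The Visit 23 window has closed if the lag exceeds 17.
- Lag: 8 to 35 days, median 19, mean 19.7.
- Last dose before Week 16: 42/112 = 37.5% past Day 17.
- Last dose from Week 16 on: 155/244 = 63.5% past Day 17. As a hand check, with 28-day spacing the lag takes each value from 8 to 35 equally often, and 18 of those 28 values exceed 17: 18/28 = 64.3%.
- All: (42 + 155)/(112 + 244) = 197/356 = 55.3%. A Day 7 or Day 9 trigger gives 51% or 60%.

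The ±7-day visit windows can stretch a nominal 28-day interval to 28 + 7 + 7 = 42 days, so real lags can be longer. They can also be shorter. The enumeration passes over visits that fall 1 to 7 days after the last dose, where compliance review (Section 6.3) might already reveal the stop.

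**The case against.** Several stronger readings are tempting, and the documents do not support them.

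- A reader might infer that nobody withdrawn under the rule can have Visit 22 on time. The rule concerns consecutive missed doses. A subject who misses 8 days, resumes and is then identified has a recent last dose, so Day 3 is feasible. It is also feasible for anyone who reports stopping at once or is stopped at a visit.
- A reader might infer that the early PWC misses abrupt discontinuation altogether. The study schedules no taper, so completers also stop abruptly, and they do have the Day 3 PWC. Only the silent, late-found stoppers are lost.
- A reader might infer that laboratory and vital sign results are similarly diluted. Both are collected at every on-treatment visit and summarised by planned assessment (Sections 11.6.2 and 11.6.3), so on-treatment values remain. The ECG has no such backup.
- A reader might take these subjects to be free of drug. The documents reviewed give no half-life; what is shown is time without a dose.

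Other objections carry some weight. Adverse events are assessed at Visit 21 and recorded up to 4 weeks after the last dose (Section 9.1), so withdrawal symptoms can still be reported. Nothing forbids a late PWC. Section 11.2 leaves detail to a separate SAP, not in the text reviewed, which may define on-treatment windows for ECGs; it could not recover a PWC that was never given. The study is uncontrolled and descriptive, so no formal inference is at risk. These points lower the severity but leave the timing conflict in place.

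**Conclusion.** The point holds for a defined group: subjects who stop study drug, do not resume, and are identified only through the missed-dose rule. For them the Day 3 PWC cannot be done in window, the plan schedules none at Visit 21, and their only scheduled post-baseline ECG, taken at least about 8 days after the last dose, is counted as end-of-treatment. These conclusions rest on the plan's own dates and survive a one-day shift in reading the trigger.

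That about 55% of last-dose days would also be past the Visit 23 window (38% before Week 16, 64% from Week 16 on) is conditional on detection at the next qualifying nominal visit and on evenly spread stopping days. It is a share of last-dose days, not of subjects. The effect on the summaries cannot be sized, because the documents give no expected number of such subjects. Severity is minor; this is a cheap improvement to the collection and labelling of two primary-endpoint components.

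**What to change.** Reconcile Sections 4.2.1, 4.2.2, 6.5.1.1 and 6.5.1.2. The withdrawal rule itself need not be touched.

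- In Sections 6.4 and 6.5, state that when the Visit 22 window has passed at first awareness, the PWC is given at that contact or at Visit 21, with days since last dose recorded.
- In Section 11.6.7, summarise the PWC by days since last dose.
- In Section 11.6.4, count the Visit 21 ECG as end-of-treatment only if it was taken within a prespecified number of days of the last dose, and list later ECGs as off-treatment.

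The cost is some protocol wording and one derivation from the date of last treatment, which Section 4.2.2 already requires. The downside is slightly fewer subjects in the ECG shift table and some PWCs at non-nominal days.

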6.5.1.2. Visit at Week 2 of Follow-up (Visit 23; Week 54)

All subjects then will return to the clinic for post-treatment follow-up approximately 14 (\pm 3) days following the last dose of study medication.

The following activities and/or assessments will be performed at the Follow-up clinic visit (Visit 23, Week 54):

- Assess for and record AEs
- Assess for and record concomitant medication use including allowable analgesics
- Record vital signs (temperature, heart rate, supine and orthostatic blood pressure) and body weight
- Perform urine pregnancy test on all WOCBP and confirm negative
- Administer the C-SSRS(See Section 9.2.1)
- Administer the PWC

Any abnormal findings (including abnormal laboratory values) observed at the End-of-Treatment visit should be rechecked at the Follow-up visit. Further safety assessments may be required for clinically significant abnormal findings observed at the Follow-up visit.

6.5.1.3. Telephone Contact at Week 4 of Follow-up (Visit 24; Week 56)

All subjects will be contacted by telephone approximately 4 weeks following the last dose of study medication. The following activities and/or assessments will be performed at this 4-week follow-up telephone contact:

- Assess for and record AEs
- Assess for and record concomitant medication use including allowable analgesics

6.6. Protocol Deviations

The investigator should conduct the study in compliance with the protocol agreed to by Sponsor and, if required, by the regulatory authority(ies), and which was given approval/favorable opinion by the IRB/IEC.

A deviation to any protocol procedure or waiver to any stated criteria will not be allowed in this study except where necessary to eliminate immediate hazard(s) to the subject. Sponsor must be notified of all intended or unintended deviations to the protocol (e.g. inclusion/exclusion criteria, dosing, missed study visits) on an expedited basis.

The investigator, or person designated by the investigator, should document and explain any deviation from the approved protocol.

If a subject was ineligible or received the incorrect dose or investigational treatment, and had at least one administration of investigational product, data should be collected for safety purposes.

The investigator should notify the IRB/IEC of deviations from the protocol in accordance with local procedures.

7. EFFICACY ASSESSMENTS

7.1. Average Daily Pain Score (ADPS)

Subjects will record their worst pain over the previous 24 hours in an electronic diary using an 11-point numeric rating scale (NRS) ranging from 0 (no pain) to 10 (worst possible pain) (refer to the Study Manual for a copy of this instrument). Pain diary scores will be recorded by the subjects during the 7 days prior to Visit 11 (Week 13), Visit 14 (Week 24), Visit 17 (Week 36), Visit 20 (Week 48), and Visit 21 (Week 52). For de novo subjects only, pain diary scores will be recorded during the 7 days prior to Visit 4 (Start-of-Treatment). During the 7 days prior to these visits, every day upon awakening, prior to taking study medication, the subject should indicate the number that best describes his or her worst pain over the previous 24 hours.⁵

For rollover subjects, the ADPS value taken from the last visit of the DS5565-A-E309, DS5565-A-E310, or DS5565-A-E311 study (i.e. End-of-Tapering) will be used as the baseline score for this study and hence will not be repeated by the subject at Visit 4 (Start-of-Treatment).

For de novo subjects, the baseline ADPS value will be calculated based on the subject's recording of pain diary scores during the Baseline period.

7.2. Patient Global Impression of Change (PGIC)

Subjects will complete the PGIC at the End-of-Treatment/Early Termination visit.

This standard instrument (refer to the Study Manual for a copy) is a well-validated outcome measure for pain treatment and shows close correlation with the 11-point pain intensity NRS in the setting of chronic pain.⁶ The 7-point PGIC measures change in the subject's overall status using the following categorical scale: 1) very much improved, 2) much improved, 3) minimally improved, 4) no change, 5) minimally worse, 6) much worse, and 7) very much worse.

7.3. Hospital Anxiety and Depression Scale (HADS)

All subjects will complete the HADS questionnaire at the Start-of-Treatment visit (Visit 4) and at the End-of-Treatment/Early Termination visit.

The HADS questionnaire is a reliable, widely-used self-assessment scale to assess symptoms of anxiety and depression.⁷ The instrument consists of 7 questions related to anxiety and 7 related to depression, each rated on a 4-point scale (score of 0 to 3). Scores for anxiety and depression are independently summed to compute HADS-Anxiety and HADS-Depression subscale scores, with ranges from 0 to 21, where higher scores indicate greater severity.

7.4. EuroQol Instrument 5 Dimensions (EQ-5D)

All subjects will complete the EQ-5D questionnaire at the Start-of-Treatment visit (Visit 4) and at the End-of-Treatment/Early Termination visit. The EQ-5D (refer to the Study

Manual for a copy) is a well-standardized instrument that shows high construct validity and responsiveness in patients with chronic pain⁸ and has been used specifically in FM.⁹ The EQ-5D includes a descriptive section with 5 dimensions (mobility, self-care, usual activities, pain/discomfort, and anxiety/depression) that are combined into an overall health utilities index, and an NRS (100 mm VAS) that measures perception of overall health, with 0 indicating worst health and 100 representing best imaginable health.

7.5. Short Form 36 (SF-36)

All subjects will complete the SF-36 questionnaire at the Start-of-Treatment visit (Visit 4) and at the End-of-Treatment/Early Termination visit. The SF-36 (refer to the Study Manual for a copy) is a generic health survey that asks 36 questions to measure functional health and well-being from the subject's point of view. It is a practical, reliable, and valid measure of physical and mental health widely used across various disease areas, including FM.¹⁰ The SF-36 provides scores for 8 health domains (physical functioning, role-physical, bodily pain, general health, vitality, social functioning, role-emotional, and mental health) as well as psychometrically-based physical component summary (PCS) and mental component summary (MCS) scores. All health domain scales contribute to the scoring of both the PCS and MCS measures.

7.6. Average Daily Sleep Interference Score (ADSIS)

Pain-associated sleep interference will be assessed using electronic diaries using an 11-point NRS ranging from 0 (pain does not interfere with sleep) to 10 (pain completely interferes with sleep, unable to sleep) (refer to the Study Manual for a copy of this instrument). The sleep interference NRS is a standard tool used to assess how pain has interfered with sleep during the past 24 hours. Sleep interference scores will be recorded by the subjects during the 7 days prior to Visit 11 (Week 13), Visit 14 (Week 24), Visit 17 (Week 36), Visit 20 (Week 48), and Visit 21 (Week 52). For de novo subjects only, sleep interference scores will be recorded during the 7 days prior to Visit 4 (Start-of-Treatment). During the 7 days prior to these visits, every day upon awakening, prior to taking study medication, the subject should complete the sleep interference question along with the pain question in the diary.

For rollover subjects, the sleep interference value taken from the last visit of the DS5565-A-E309, DS5565-A-E310, or DS5565-A-E311 study (i.e. End-of-Tapering) will be used as the baseline score for this study and hence will not be repeated by the subject at Visit 4 (Start-of-Treatment).

For de novo subjects, the baseline sleep interference value will be calculated based on the subject's recording of sleep interference scores during the Baseline period.

